Thus, study participation will include the two study sessions, completion and recording of exposures for one week between study sessions, and completion of a study-assigned exposure in a subsequent Clinic therapy session. Participation consent and assent will include agreement for clinically gathered assessments to be used for the study (i.e., initial structured interview, symptom rating scales completed at initial evaluation and clinic treatment follow up, number of treatment sessions attended, length of treatment). Study participants will continue with any treatment as usual during study participation.

Participant Recruitment & Participation Flow

Initial Clinic visit	Baseline Study Visit	1 week out-of-session exposure	Follow up Study Visit	Next Therapy Session	End of treatment assessments
Complete diagnostic interview & questionnaires as part of usual clinic procedures; If the patient meets study criteria, the Clinic psychologist/therapist will invite the patient and parent to participate	Informed Consent/Assent. 2 Baseline exposures. Participant will wear a sensor to obtain biometrics and SUDS ratings will be collected.	Participants will be instructed to practice daily either the VR exposure or imaginal exposure, depending on study condition, and to record exposures using the exposure tracking form	Repeat 2 baseline exposures. Participant will wear a sensor to obtain biometrics and SUDS ratings will be collected. Participants assigned generalization exposure to complete in next therapy session Qualitative interview and observation. Complete the Spence Child Anxiety Scales and the Child Sheehan Disability Scale. Participant will wear a sensor to obtain biometrics.	Participant will complete the assigned generalization exposure during therapy session following the Follow up Study Visit Participant will wear a sensor to obtain biometrics and SUDS ratings will be collected.	Participants complete questionnaires as part of usual clinic procedures. Study staff records data related to treatment length and # treatment sessions. Post-Treatment from Clinic
Participants continue with any treatments as usual, including treatment through Clinic					

Statistical Analysis Plan

Analysis Plan

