The primary outcomes of the study are: (1) difference in maximum SUDS ratings during time 1 exposures between VR and conventional, 2) difference in number of exposures completed to assigned item (as well as overall) between conditions; 3) difference in maximum SUDS rating in cross over exposure between conditions during time 2; and 4) difference in maximum SUDS rating in generalization exposure between conditions during time 2. We will also conduct exploratory analyses to see if decrease in anxiety symptoms, as measured by the Spence Child Anxiety Scales, Child and Parent reports, and improvement in functional impairment, as measured by the Child Sheehan Disability Scale, differ between groups.

Quantitative analysis: Descriptive and inferential statistics will be used, including means, standard deviations, medians, ranges, frequency distributions, t-tests, and Analyses of Variance (ANOVAs). Specifically: a) differences in maximum SUDS ratings during VR and traditional exposures during time 1 session will be examined using a paired-samples t-tests, b) change over time in the peak anxiety ratings for each modality (VR vs. imaginal) will be examined using Repeated Measures ANOVAs with VR status as the between subjects variable and change in anxiety rating (T1 to T2 difference in maximal SUDS for VR vs. T1 to T2 difference in maximal SUDS for imaginal) being the within subjects variable, c) differences between homework exposure conditions, on maximal anxiety in the generalization exposure at time 2 controlling for time 1 maximal SUDS averaged across exposure conditions will be examined using Analyses of Covariance (ANCOVA) with homework condition as the between subjects variable and number of completed exposures and average maximum anxiety across the two time 1 exposures as the covariates; and d) ANCOVA will be used to compare average number of homework exposures completed to target item (as well as overall exposures) during the study time frame between the conditions (i.e. VR vs. imaginal) controlling for patient characteristics (age, sex, diagnoses). Exploratory analyses will compare change in anxiety symptoms from time 1 to time 2 between conditions, controlling for patient characteristics, and examining number of completed exposures as a mediator of change.

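### Exploratory Sheehan improvement and Spence change from time 1 to time 2 are planned, but neither scale is scheduled at the Baseline Study Visit

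*Combined protocol and SAP*

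**What the plan says.** The Analysis Plan lists exploratory comparisons on two questionnaires. One is the Spence Child Anxiety Scales, child and parent report. For the other, the question is whether "improvement in functional impairment, as measured by the Child Sheehan Disability Scale, differ between groups". The quantitative analysis paragraph adds that these analyses will "compare change in anxiety symptoms from time 1 to time 2 between conditions", adjusting for patient characteristics and "examining number of completed exposures as a mediator of change". The same paragraph attaches time 1 to the session with the two baseline exposures: "differences in maximum SUDS ratings during VR and traditional exposures during time 1 session".

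The Participant Recruitment & Participation Flow table gives the content of each visit:

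- Initial Clinic visit: "Complete diagnostic interview & questionnaires as part of usual clinic procedures". The questionnaires are not named there. The opening Study Protocol section does name the Spence, both reports, as part of the diagnostic assessment.
- Baseline Study Visit: "Informed Consent/Assent. 2 Baseline exposures. Participant will wear a sensor to obtain biometrics and SUDS ratings will be collected".
- Follow up Study Visit, one week later: "Complete the Spence Child Anxiety Scales and the Child Sheehan Disability Scale".

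The consent covers study use of clinic data, including "symptom rating scales completed at initial evaluation and clinic treatment follow up".

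**The concern.** Improvement and change both need a starting value. The table names both scales at follow-up and neither at baseline, and the prose account of the baseline session adds neither. The Sheehan is named at no visit before follow-up. The Spence has an earlier named score, but it comes from before psychoeducation and treatment planning, at an unstated distance from the baseline session.

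Two things are at stake. The first is precision: without a time 1 score, the exploratory comparisons cannot adjust for where each child stood when the homework week began. Elsewhere the plan makes this kind of adjustment, since the generalization analysis takes time 1 SUDS as a covariate. The second is interpretation: a report could present Spence change as one week's change when it also contains earlier clinic care, and the mediation analysis would inherit that mismatch.

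**Working it through.** The documents give no sample size, standard deviation, correlation or allocation ratio, so there is no planned figure to reproduce.

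**1. Where each scale is named**

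| Point in the study | Spence | Child Sheehan |
|---|---|---|
| Initial clinic assessment | named, both reports | not named; some questionnaires are not itemised |
| Psychoeducation and treatment planning (length not stated) | none named | none named |
| Baseline Study Visit | not scheduled | not scheduled |
| Follow up Study Visit, 1 week later | scheduled | scheduled |

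From the named measurements, Spence change runs from the initial assessment to follow-up: the unstated gap plus 1 week. Sheehan improvement has a named end and no named start.

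**2. Sheehan precision**

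Assumptions: 1:1 arms, equal variance at both times, no clinic Sheehan available, and correlation r between time 1 and time 2 after any other covariates. The time 2-only variance of the arm difference is set to 1.

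- ANCOVA on the time 1 score: 1 − r²
- Plain change score: 2(1 − r)
- Interval width, ANCOVA against time 2 only: √(1 − r²)
- Extra participants that time 2 only needs to match ANCOVA: 1/(1 − r²) − 1

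| Assumed r | ANCOVA variance | Change-score variance | Interval ratio (ANCOVA) | Extra participants |
|---|---|---|---|---|
| 0.4 | 0.84 | 1.20 | 0.92 | 19% |
| 0.6 | 0.64 | 0.80 | 0.80 | 56% |
| 0.7 | 0.51 | 0.60 | 0.71 | 96% |

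The change score beats time 2 only when 2(1 − r) < 1, that is, when r > 0.5. At r = 0.4 it is worse, with 20% more variance.

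Estimating the baseline slope costs a little. With total size N the ANCOVA variance becomes (1 − r²)(1 + 1/(N − 4)). At an assumed N = 20 this is 0.892, 0.680 and 0.542; at N = 60 it is 0.855, 0.651 and 0.519. Fitting patient characteristics as well would use further degrees of freedom, which this factor ignores.

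**3. Spence precision**

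Here an earlier score exists, so the comparison is between adjusting for the initial-evaluation score and adjusting for a time 1 score. The variance ratio is (1 − r_new²)/(1 − r_old²).

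- Gap short, correlations equal: ratio 1, no gain.
- 0.6 to 0.7: 0.51/0.64 = 0.80, a 20% reduction (interval 0.89 times as wide).
- 0.4 to 0.6: 0.64/0.84 = 0.76, a 24% reduction (interval 0.87 times as wide).

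**4. Mediation**

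Change from initial assessment to time 2 is the sum of change before the baseline session and change during the study week. Homework exposures are recorded only in the second part and cannot have caused the first. Randomisation balances the first part between arms in expectation, but not across exposure counts, because those are not randomised. A child who had already improved might do more exposures or fewer. The size and direction of the distortion cannot be derived from the documents.

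**The case against.** The strongest reply is that the plan may already have its baselines. All patients complete the Spence before randomisation, consent covers its reuse, and it can serve as an ANCOVA covariate. The Sheehan may be among the clinic's unnamed questionnaires. The opening section's list of assessments is introduced as a partial one, and the exclusion criteria mention a self-report measure that appears in neither that list nor the flow table. This stands as far as it goes. A reader might infer that no Sheehan baseline exists and that improvement can never be calculated. The documents do not support that; they show only that none is named. A clinic Sheehan from the initial visit would, however, also predate the baseline session.

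A second reply is that time 1 is never defined for the questionnaires. The labels are indeed loose: the generalization exposure is assigned to time 2, yet it takes place at the therapy session after follow-up. A reader might infer that the Spence window is plainly misstated. That holds only if time 1 means the baseline session, as the SAP uses the term for the exposures. If it means the initial assessment, the change still includes earlier care, and the SAP does not say so.

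A third reply is that the precision gain belongs partly to ANCOVA, which the exploratory plan does not name. That is correct: read as a plain change score, Sheehan improvement would be less precise than a time 2 comparison at r = 0.4. It is therefore too strong to say that the missing time 1 score costs precision whatever the analysis.

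**Conclusion.** The concern holds as a schedule that does not supply what the exploratory analyses name. No starting value is named for Sheehan improvement. If time 1 is the baseline session, the computable Spence change covers more than the study week, and the mediation analysis relates one week of exposures to change that partly came before it.

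A reader might infer that the randomised comparisons are biased. They are not: a time 2 Sheehan contrast still estimates the arm difference, and Spence change before randomisation is expected to be equal in both arms. The primary SUDS and exposure-count outcomes are untouched.

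The loss is precision and interpretability in exploratory analyses. If no clinic Sheehan exists, ANCOVA on a time 1 score would lower variance by 16%, 36% or 49% at r = 0.4, 0.6 or 0.7, before the small cost of estimating the slope. For the Spence the gain may lie anywhere from near zero to about 24%. Every correlation and sample size here is assumed. The point is worth correcting because it costs little, but it does not threaten the main results.

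**What to change.** Give the Spence (child and parent) and the Child Sheehan at the Baseline Study Visit, after consent and assent, before allocation is revealed and before the exposures begin. The order needs care: the protocol text randomises after consent and before the baseline session, while the flow table places consent at that same visit. Analyse time 2 scores by ANCOVA on the time 1 score, not as plain change scores, and keep the planned patient characteristics. Use the time 1 score in the mediation model too, and report that model as observational, since a baseline score does not remove confounding of a non-randomised mediator.

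The cost is extra questionnaire time for child and parent at a visit already put at about 90 minutes, and withholding allocation until the forms are complete. Both scales are already in use at follow-up.

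If data are already collected, SAP wording is enough. Define time 1 for the questionnaires. Adjust the time 2 Spence for the initial-evaluation Spence, state the true window, and limit the mediation claim accordingly. Describe the Sheehan analysis as a time 2 comparison between arms, or adjust it for a clinic baseline if one was collected and is named.

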will be familiar with parent-coached exposure procedures. Standard Clinic treatment includes parent-coached exposure in and between sessions. For the study baseline session, a Clinic psychologist/therapist will follow the standardized protocol to guide all participants through planning two exposures related to content from their personalized fear ladder, one with the VR system and an analogous imaginal exposure (order randomized). Parent-child dyads will complete these exposures in session with study staff present (in most cases, the research coordinator). During each exposure, the participant will record his or her anxiety using a 0 to 10 SUDS rating scale, the standard procedure during clinical care and between-session exposures. For the VR exposure, the staff member will ask the participant to follow instructions presented by the VR program. The conventional exposure will follow common clinical practice for imaginal exposures; specifically, the participant will write a story about their fears coming true and then read the story aloud. In each condition, the staff member will encourage the participant to repeat the exposure until anxiety ratings are reduced by 50%. Based on clinical experience and confirmed during earlier research, it is anticipated that participants' anxiety will be manageable throughout the exposure and will have habituated by the end of the exercise. Each of the study sessions will be approximately 90 minutes. In the unlikely event of difficulties during a study session, and in accordance with the safety monitoring plan, the lead psychologists will be available to evaluate the participant, address emotional distress, and arrange appropriate care. Throughout the course of the study (i.e., between study sessions), participants will have access to the lead psychologists as well as the supports of typical clinical care including the treating therapist, or a covering clinician through the Clinic Division of Child Psychiatry and Psychology will be available for research participants 24 hours a day, 7 days a week. The exposure activity and SUD ratings for each exposure will be recorded on paper with the exposure tracking form. Each participant will be asked to wear a sensor on their wrist during the in-office exposures. These sensors are similar to an activity tracker. The sensors will measure real-time physiological data (i.e. heart rate, acceleration, body temperature, etc). This information will allow the study team to note changes with the patient as they participate in the exposures. It will also provide valuable data that can be analyzed at the end of the study. These sensors do not collect any patient health information. The sensors will either Empatica E4 but in the event the study team cannot get the Empatica 4, they will use the Elite HRB CorSense.

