
Participants will then be assigned one week of daily exposure homework with or without VR, depending on condition, using a paper exposure tracking form to record each exposure and SUDS. Patients randomized to intervention will take home the VR system for homework completion, and participants assigned to control will not take the VR system home and will be instructed to complete imaginal exposures. Participants will be asked to record each exposure, even if it is not related to the fear addressed with the baseline exposures, in order to capture all exposures completed during the homework period.

One week after the baseline session, all participants will return for a follow up session in which they complete both types of exposure (order randomized) and will receive an assignment to complete in their next Clinic therapy appointment a third generalization exposure, i.e., an exposure related to the baseline exposure that is higher on the fear ladder for the targeted fear, following procedures analogous to the baseline session. During the follow up session, staff from Clinic Health Care Policy & Research ("the interviewer") experienced in qualitative data analysis and not involved with the patients' medical care or development of the prototype system will observe, record, and code participants' engagement in the exposures and will interview participants about their experience with both types of exposure and then will ask for observations and opinions from the parent. A psychologist from the Clinic Health Care Policy & Research will work with the two lead child psychologists to identify questions and topics for a

semi-structured interview guide. The guide will be pilot-tested to ensure that questions and follow-up probes are easily comprehended and delivered in a sensitive manner. The semi-structured guide will follow guidelines for minimizing bias and increasing the reliability and validity of interview data[64,65]. All interviews will be audio-recorded.

During the participants' next therapy session, they will complete the assigned generalization exposure. SUDS ratings will be recorded for that exposure using the paper exposure tracking form, and participants will wear a sensor to obtain biometrics during the exposure.

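### Primary outcome 1: the paired t-test omits the randomized VR/imaginal order, which costs power if peak SUDS falls by about 1 point or more between the two exposures

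*Combined protocol and SAP*

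**What the plan says.** The first listed primary outcome (Statistical Analysis Plan, Analysis Plan) is the "difference in maximum SUDS ratings during time 1 exposures between VR and conventional". Under Quantitative analysis, item (a) gives the test: "differences in maximum SUDS ratings during VR and traditional exposures during time 1 session will be examined using a paired-samples t-tests". None of the analyses listed there contains an order, period or sequence term.

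The Study Protocol section describes the baseline session as two planned exposures, "one with the VR system and an analogous imaginal exposure (order randomized". During each one "the participant will record his or her anxiety using a 0 to 10 SUDS rating scale". Both take place in a single visit: "Each of the study sessions will be approximately 90 minutes". On repetition within an exposure it says: "In each condition, the staff member will encourage the participant to repeat the exposure until anxiety ratings are reduced by 50" per cent. It expects that anxiety "will be manageable throughout the exposure and will have habituated by the end of the exercise".

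At the follow-up visit the order is again described as randomized: "they complete both types of exposure (order randomized". The documents do not say whether order is blocked or drawn by simple randomization, or whether the follow-up order is a new draw.

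**The concern.** The two baseline exposures use related content from the same child's fear ladder and are done in one sitting. The second starts after deliberate habituation in the first, so a lower peak in second place is plausible. The documents expect anxiety to fall within an exposure. They do not say that the peak of the next exposure falls, nor by how much.

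If it does fall, children who start with VR have a VR-minus-imaginal difference shifted upward, and children who start with imaginal have it shifted downward. A plain paired t-test treats this systematic spread as random error. A real modality difference in the first listed primary outcome is then more likely to be missed than it needs to be, although the design already supplies the factor that would remove the spread.

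**Working it through.** **Inputs.** From the documents: a paired comparison, randomized order and a 0 to 10 scale. Not in the documents, so assumed: n = 20 to 60; within-order SD of the difference (sd) 2.0 to 3.0; true modality difference τ = 1.2; drop in peak from first to second exposure π = 0 to 2; two-sided 5% test. The plan gives no power figure to reproduce.

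**Model.** For each child, D = VR peak − imaginal peak = τ + sπ + e, where s = +1 if VR is first and −1 if imaginal is first. Hence:

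- paired t-test: Var(D) = sd² + π²
- with an order term: residual variance sd²
- variance ratio: 1 + π²/sd²

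With sd = 2.5, the ratio is 1 + 1/6.25 = 1.16 at π = 1 and 1 + 4/6.25 = 1.64 at π = 2. At n = 40 and π = 2 the SD of the estimate under simple randomization is √(10.25/40) = 0.51 for the paired test, against about √(6.25/40) = 0.40 with the order term.

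**Power.** Simulated with 40,000 replicates per cell, sd 2.5, τ = 1.2, simple randomization of order. Entries are paired t / order-adjusted, in %:

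| n | π = 0 | π = 0.5 | π = 1 | π = 2 |
|---|---|---|---|---|
| 20 | 53 / 51 | 52 / 51 | 47 / 51 | 35 / 51 |
| 30 | 72 / 71 | 70 / 70 | 66 / 70 | 51 / 70 |
| 40 | 84 / 83 | 83 / 83 | 78 / 83 | 63 / 83 |

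At n = 60 the figures are 93 / 95 (π = 1) and 81 / 95 (π = 2). At n = 40 and π = 1.5 they are 72 / 83.

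**Range over sd, n = 40.** For sd 2.0: 91.4 / 95.5 (π = 1) and 74.4 / 95.5 (π = 2). For sd 3.0: 64.7 / 68.1 and 53.8 / 68.4.

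**Break-even.** The paired test is marginally better when π is below roughly sd/√n: 2.5/√20 ≈ 0.6, 2.5/√30 ≈ 0.5, 2.5/√40 ≈ 0.4, 2.5/√60 ≈ 0.3.

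**Balanced order.** If the two orders are forced equal, the order shifts cancel in the mean, but the paired test still counts them in its standard error and becomes conservative. At n = 40 its type I error is 3.5% (π = 1) and 1.2% (π = 2), and power is 80 / 84 and 66 / 84. Under simple randomization its type I error stays at 5.0% and 4.9%.

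**Chance imbalance.** A single trial's unadjusted estimate shifts by π(n₁ − n₂)/n. At n = 40, 27% of simple draws are 24:16 or worse, a shift of at least (8/40)π = 0.2π. At n = 20, 26% are 13:7 or worse, a shift of at least (6/20)π = 0.3π.

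**Sensitivity to the effect size.** Further runs (10,000 per cell) set τ = sd(1.96 + 0.84)/√n, for nominal 80% power. At n = 40, balanced order and π = 1, power rises from 63.7 to 77.5% (sd 1.5), 71.2 to 78.8% (sd 2), 72.6 to 77.7% (sd 2.5) and 74.8 to 78.3% (sd 3).

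**Analysis (b), secondary.** This concerns the group-by-modality term, with 20 per arm, SD of the difference between the two changes 3.54, and an effect of 3.2 chosen to give about 80% power. If order is redrawn at time 2, power without and with order terms is 80 vs 77% (π = 0), 78 vs 77% (0.5), 73 vs 77% (1) and 58 vs 77% (2). If each child keeps the same order and the drop is equal at both visits, it cancels and nothing is lost.

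**The case against.** A paired t-test with randomized order is a legitimate analysis, and nothing in the documents contradicts it. The expected habituation is within an exposure, whereas the endpoint is the maximum rating, so a lower second peak is an inference. Sample size, SD, true difference and drop are all assumed. This stands, and it is why the point is about efficiency.

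One point is where the gain begins, not where it becomes large. With simple randomization, τ = 1.2 and a 1-point drop, the gain is 3.6, 4.7, 4.8 and 2.7 percentage points at n = 20, 30, 40 and 60 for sd 2.5, and 1.8, 2.6, 3.3 and 3.0 points for sd 3.0. In the sd 2.5 runs, gains near 10 points or more need a drop of 1.5 to 2. This also stands.

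The chance-imbalance argument adds little. At 24:16 and π = 1 the shift is 0.2, against a standard error of √(7.25/40) = 0.43, and under simple randomization the paired test's standard error already covers that variation.

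The order term assumes the same drop whichever modality comes first. Carry-over that differs by modality is plausible and the term does not remove it. The paired test does not remove it either, so this limits the remedy without favouring the current plan.

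Finally, the documents say order is randomized but not that it is kept as an analysis variable. That is fair, and the fix should cover it.

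**Conclusion.** The concern holds as a matter of precision. The trial randomizes order and then leaves it out of the test of its first listed primary outcome. The paired test is valid on average, and conservative if orders are balanced. For sd 2.5 to 3 and simple randomization, the order term gains about 2 to 5 points of power at a 1-point drop. At a 2-point drop and n = 40 it gains about 15 to 21 points over sd 2.0 to 3.0. At 0.5 or less it gains nothing material.

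These sizes rest on assumed n, SD, true difference and drop, on an additive order effect, and on ratings simulated as continuous normal values without the bounds of the 0 to 10 scale. Confidence is medium because the drop is unknown. The change is still worth making, since the possible gain is much larger than the cost.

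**What to change.** In analysis (a), regress each child's VR-minus-imaginal difference in maximum SUDS on order, coded +1 (VR first) and −1 (imaginal first), and test the intercept as the modality effect. A mixed model with modality and period is an alternative. State whether order is blocked or simple, and that it is kept in the analysis dataset.

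The cost is SAP wording and one degree of freedom. With no order effect and simple randomization, power goes from 84 to 83% at n = 40 and from 53 to 51% at n = 20. With balanced orders the cost is essentially nil.

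For (b), state whether order is redrawn at time 2. If it is, add time 1 and time 2 order to the modality and group-by-modality terms, at a cost of two degrees of freedom and about 2 points of power at n = 40 with no order effect. If each child's order is fixed and the drop is equal at both visits, (b) needs no change. These terms are not shown to test a listed primary outcome, so this part is secondary.

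A comparison of first-position exposures only could be added as a check on unequal carry-over, labelled as low-powered. For a difference of 1.2 and a single-rating SD of 2.0, 2.5 or 3.0, its power is 46, 32 or 23% at n = 40 and 25, 17 or 14% at n = 20, so a null result would not be informative.

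### Item b compares the arms on raw T1-to-T2 change in maximum SUDS; adjusting T2 for the T1 rating already collected would usually be more precise, at little cost

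*Combined protocol and SAP*

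**What the plan says.** The Analysis Plan lists four primary outcomes. The third is the "difference in maximum SUDS rating in cross over exposure between conditions during time 2". Of the four listed quantitative analyses, only item b uses T2 SUDS from the two repeated exposures. Item a uses time 1 only, item c concerns the generalization exposure, and item d counts homework exposures. The exploratory analyses concern symptoms and impairment.

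Item b specifies "Repeated Measures ANOVAs with VR status as the between subjects variable", and the within-subjects variable is "change in anxiety rating (T1 to T2 difference in maximal SUDS for VR vs. T1 to T2 difference in maximal SUDS for imaginal". It names no covariate. I read VR status as the randomised homework arm.

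The data for an adjusted analysis are already collected. On the scale, the Study Protocol section says that "the participant will record his or her anxiety using a 0 to 10 SUDS rating scale". In the participation flow table the baseline visit has "2 Baseline exposures. Participant will wear a sensor to obtain biometrics and SUDS ratings will be collected", and the follow-up visit has "Repeat 2 baseline exposures". Each child should therefore have a T1 and a T2 maximum for VR and for imaginal exposure.

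**The concern.** A change score subtracts T1 with a fixed weight of 1. When arms are randomised, the most efficient weight is the regression slope of T2 on T1, which for a noisy rating with similar spread at both visits is below 1. Fixing it at 1 carries extra T1 noise into the arm comparison. It also over-corrects any chance T1 difference between arms (regression to the mean).

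Reading the ANOVA as having time as a within-subjects factor makes no difference. With two visits and complete data, the arm-by-time test is the test on change averaged over modalities, and the arm-by-time-by-modality test is the test on the difference between the two changes.

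What is at stake is precision: wider intervals and lower power from the same children and the same ratings, in the one analysis available for primary outcome 3. That outcome is also worded as a time 2 difference, which adjusted T2 matches more directly than change does.

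**Working it through.** **Inputs.** From the documents: a 0-10 rating, two modalities, the same two exposures at T1 and T2, and two randomised arms. Not in the documents, and so assumed: the T1-T2 correlation ρ (0.2 to 0.8), the SD ratio k = SD(T2)/SD(T1) (1, then varied), and the sample size. The plan states no power or sample-size figure that could be reproduced.

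**Step 1: equal SDs.** Let s be the common SD. Per child, the variance that drives the arm comparison is
- change score: 2(1−ρ)s²
- T2 adjusted for T1 (ANCOVA): (1−ρ²)s²

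The ratio ANCOVA/change is (1−ρ²)/[2(1−ρ)] = (1+ρ)/2, so the information lost by the change score is (1−ρ)/2.

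| ρ | change /s² | ANCOVA /s² | information lost | children needed, change ÷ ANCOVA |
|---|---|---|---|---|
| 0.2 | 1.60 | 0.96 | 40% | 1.67 |
| 0.3 | 1.40 | 0.91 | 35% | 1.54 |
| 0.5 | 1.00 | 0.75 | 25% | 1.33 |
| 0.7 | 0.60 | 0.51 | 15% | 1.18 |
| 0.8 | 0.40 | 0.36 | 10% | 1.11 |

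Below ρ = 0.5 the change-score variance exceeds s², so it is noisier than T2 alone.

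**Step 2: unequal SDs.** The loss is 1 − (1−ρ²)k²/(1+k²−2ρk). At ρ = 0.5:
- k = 0.7: 1 − 0.75×0.49/0.79 = 53%
- k = 1.25: 1 − 0.75×1.5625/1.3125 = 11%

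Over ρ = 0.2 to 0.8 the loss is 51-61% at k = 0.7 and 0-27% at k = 1.25. It reaches zero where ρk = 1, for example 0.8 × 1.25, because the efficient slope is then 1, the weight that the change score uses.

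**Step 3: item b's two between-arm tests.** Assume equal SDs and correlations of 0.6 (same modality across visits), 0.4 (different modality across visits) and 0.5 (between modalities within a visit).
- Arm effect, from the mean of the two modalities: ρ = (0.6+0.4)/(1+0.5) = 0.67, loss 17%.
- Arm-by-modality effect, from the VR-minus-imaginal difference: ρ = (0.6−0.4)/(1−0.5) = 0.40, loss 30%.

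A simulation with these correlations (10,000 runs) gave losses of 13% and 28% at 40 children in total, and 16% and 27% at 60. Over six assumed sets of correlations, the closed form gave 12.5-28% for the arm effect and 20-40% for arm-by-modality.

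**Step 4: cost of estimating the slope.** Multiplying the ANCOVA variance by about 1+1/(N−4), with N = 40 in total, leaves losses of 38%, 23% and 7.5% at ρ = 0.2, 0.5 and 0.8. The advantage disappears only at very small N with very high ρ: at N = 20 and ρ = 0.9, ANCOVA is about 1% worse.

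**Step 5: illustration.** Assume a true difference of 0.5 SD, two-sided 5% and equal SDs.

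| ρ | n per arm for 80% power, change vs ANCOVA | power at 30 per arm, change vs ANCOVA |
|---|---|---|
| 0.2 | 101 vs 61 | 33% vs 51% |
| 0.5 | 63 vs 48 | 49% vs 61% |
| 0.8 | 26 vs 23 | 87% vs 90% |

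**The case against.** The strongest defence is that item b is a legitimate analysis of the question it names. It sets out to study change in each modality, and its within-child comparison asks whether peak anxiety falls more for one modality than for the other. A regression of T2 on arm and T1 does not test that. This stands, so item b should not be replaced as a whole.

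Second, randomisation comes before the T1 session (Study Protocol section after Study Population), and the documents do not say that allocation is hidden until T1 has been rated. If knowing the allocation shifts ratings by a constant d at both visits, the change score cancels the shift. ANCOVA with slope b leaves d(1−b), which is half the shift at b = 0.5. If only T1 is shifted, the order reverses: the change score is off by d in size and ANCOVA by bd. Neither scenario is documented, and home practice differs only after T1, so this does not favour raw change in general. It does mean that adjustment carries an assumption of its own, and it justifies a sensitivity analysis.

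Third, the size is unknown. This stands: every percentage here depends on assumed correlations and SDs. A wider spread at T2, plausible if response to homework varies, would shrink the loss.

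A reader might also infer that item b contradicts item c, which works on maximal anxiety in the generalization exposure, "controlling for time 1 maximal SUDS averaged across exposure conditions". The documents do not support that. The generalization exposure is a third exposure, assigned at follow-up, with no T1 rating of its own, so no like-for-like change score can be formed. The two methods differ because the data differ.

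**Conclusion.** The point holds as one of efficiency. Item b's arm and arm-by-modality tests use raw change, the T1 ratings needed for adjustment are already collected, and in large samples under randomisation the adjusted analysis is never less precise. With equal SDs and ρ of 0.2 to 0.8, the loss is about 40% down to 10%. It is about 0-27% if the T2 SD is 1.25 times the T1 SD, and 51-61% if it is 0.7 times. These are conditional ranges, not properties of this trial. Under comparable correlation assumptions, the arm-by-modality test loses more than the arm test.

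A reader might infer that the change-score comparison is invalid or biased. It is not: if allocation does not affect T1 ratings, the arms have the same expected T1, so the expected difference in change equals the expected difference in T2. This is a recommended improvement, not an error that undermines the conclusions.

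**What to change.** Change the SAP wording for item b's between-arm tests only:

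1. Arm effect: regress the child's mean of the two T2 maxima on arm plus the mean of the two T1 maxima.
2. Arm-by-modality effect: regress the child's T2 VR-minus-imaginal difference on arm plus the T1 VR-minus-imaginal difference.
3. Primary outcome 3: for each modality, regress the T2 maximum on arm plus the same-modality T1 maximum. The first two models average or difference the modalities, so neither isolates one exposure. The SAP should say which contrast answers outcome 3, since the documents do not define the cross over exposure.
4. Keep the planned repeated measures ANOVA for the within-child modality effect on change.
5. Report the change-score arm comparison as a sensitivity analysis, and say whether children and staff knew the allocation when T1 was rated.

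If item b has already been run, add the adjusted models and label them as added later.

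Cost: no new data, visits or children, and one degree of freedom per model. The adjusted models assume a linear, common slope on a bounded 0-10 scale. If knowledge of allocation shifts ratings equally at both visits, they keep part of a bias that the change score would cancel.
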